5.2.7 Infectious Disease Risk

In general, higher risk for infections has not been a concern during the clinical use of imatinib. Nevertheless, all participants will undergo careful surveillance during the initial phase of the study. Baseline analyses will determine whether the participant has had a primary infection with EBV, CMV, or varicella. At each visit, participants will be assessed for signs and symptoms of new or reactivating infections. If there are concerns, including pyrexia of unknown origin, participants will be evaluated for

opportunistic infections, including PCR monitoring for EBV and CMV. If a diagnosis of a new or reactivating infection that is clinically significant is confirmed, imatinib treatment will be discontinued until successful treatment and resolution of the infection. In conjunction with an infectious disease consultation, reintroduction of imatinib will be considered.

5.2.8 Pregnancy

Site staff will regularly review the concerns regarding avoidance of pregnancy with participants during the course of the study, especially during the initial 6 months on therapy. Urine pregnancy tests will be conducted at baseline and every following visit while on study drug. Male participants are to use birth control at least 3 months after study drug discontinuation. If, despite these measures, a participant becomes pregnant, imatinib will be permanently discontinued and the participant will be counseled on potential risks to the fetus. Pregnancies of partners of male participants will also be followed.

Given the potential risk to the fetus, while on study drug/placebo, women of child-bearing potential, defined as all women physiologically capable of becoming pregnant, must agree to use highly effective methods of contraception.. This contraception should start 1 week or more prior to the start of study drug/placebo (noting that the terminal half-life of imatinib is approximately 18 hours, and 5 times this duration is 90 hours or ~4 days)) and continue during the subsequent 6 months of study drug/placebo dosing ***Highly effective contraception methods include:***

- Total abstinence (when this is in line with the preferred and usual lifestyle of the subject). Periodic abstinence (e.g., calendar, ovulation, symptothermal, post-ovulation methods) and withdrawal are not acceptable methods of contraception
- Female sterilization (have had surgical bilateral oophorectomy with or without hysterectomy) or tubal ligation at least six weeks before taking study treatment. In case of oophorectomy alone, only when the reproductive status of the woman has been confirmed by follow up hormone level assessment
- Male sterilization (at least 6 months prior to screening). For female subjects on the study the vasectomized male partner should be the sole partner for that subject
- Combination of any two of the following (a+b or a+c, or b+c):
 - a. Use of oral, injected or implanted hormonal methods of contraception or other forms of hormonal contraception that have comparable efficacy (failure rate <1%), for example hormone vaginal ring or transdermal hormone contraception
 - b. Placement of an intrauterine device (IUD) or intrauterine system (IUS)

- c. Barrier methods of contraception: Condom or Occlusive cap (diaphragm or cervical/vault caps) with spermicidal foam/gel/film/cream/vaginal suppository

In case of use of oral contraception women should have been stable on the same pill for a minimum of 3 months before taking study treatment.

5.2.9 Bone and Mineral Metabolism

Small clinical studies in oncology have identified effects on bone metabolism. Further, in a pilot animal study there is a possible effect of imatinib on growth plate architecture, and in a few case reports and a retrospective analysis of children with CML there is a possible effect of therapy on growth rate (see section 1.5.1.11). Therefore, biochemical markers of bone metabolism will be measured in all subjects. At Visit 0, all subjects less than 18 years of age will have their bone age assessed using the Fels method (plain film) by a central reader who is an expert in skeletal maturation in order to determine their bone age and growth potential. Female subjects with a bone age of less than 14 years and male subjects with a bone age less than 16 years will be considered to have significant remaining growth potential at study entry and referred to in this protocol as a “growing-age participant”. Growth assessments will be performed according to the Schedule of Events.

Growing-age participants will have their Ht-SDS determined via standard reference charts published by CDC (2001). Additional factors that commonly affect growth will be evaluated at regular intervals, to distinguish the potential contribution from these issues versus those that may be attributed to study drug.

Phosphorous and vitamin D supplementation may be needed if any deficiencies are noted, as suggested by Berman et al.¹⁵² Given the relatively short-term course of therapy, we do not expect any long-term problems with bone metabolism.

5.2.10 QT Prolongation

All participants will have electrocardiograms (ECGs) performed at Visit -1 (screening) and Visit 1. Participants will not be eligible for the study if QTc is > 450 ms in males or >470 ms in females at Visit -1, If QTc is >480 ms or there is > 60 ms change from the Visit -1 ECG, then study drug will be discontinued. Participants experiencing dizziness or syncope greater than a grade 2 should promptly seek medical attention and obtain an ECG and electrolytes.

5.3 DISCONTINUATION OF STUDY MEDICATION IN AN INDIVIDUAL PARTICIPANT

Study medication according to study specifications will be discontinued for an individual participant if *any* of the following occurs:

- A discontinuation criterion for imatinib, as noted in section 5.2, is met.
- Clinical evidence of cardiac toxicity, such as congestive heart failure or significant cardiac arrhythmias, is observed.
- Pregnancy occurs.
- A severe or serious AE occurs, which, based on the medical judgment of the investigator, prevents a participant from completing the study treatment (see section 8 for classification of AEs).
- The investigator determines that it is in the participant's best interest to discontinue treatment.
- The participant, or participant's legal representative, requests that treatment be halted.

Further care will be provided according to the judgment and practice of the investigator.

The participant will be asked to remain in the study and participate in follow-up. If study treatment is discontinued, the medical monitor should be notified.

5.4 CONCOMITANT MEDICATIONS

Any participants who need to start a concomitant medication, for whatever reason, should contact the study team to review its potential effects on imatinib metabolism. Those who require an emergency therapy will be encouraged to pursue the necessary clinical care, but then contact the study team within 24 hours to review the potential effects on imatinib metabolism. Whenever possible, the recommendation will be to use concomitant medications that do not alter imatinib levels.

5.4.1 Prohibited Medications

Use of cytochrome P450 inducers/inhibitors, unless considered essential by the investigator, are prohibited during the treatment phase. Imatinib is metabolized by the CYP3A4/5 cytochrome P450 enzyme system, and drugs that induce or inhibit this enzyme may alter imatinib levels (see section 1.5.1.12 for a list of inducers and inhibitors).

5.5 DRUG ACCOUNTABILITY

Under federal regulations (21CFR 312.62) an investigator is required to maintain adequate records of the disposition of the investigational product, including the date and quantity of drug that was received, the participants to whom drug was dispensed

(participant by participant accounting), and an account of any drug accidentally or deliberately destroyed. The investigator will ensure that the investigational product supplies are stored as specified in the protocol and pharmacy manual in a secured area, with access limited to authorized study personnel as described in the clinical study agreement.

Records for receipt, storage, use, and disposition of the study drug will be maintained by the study sites. A drug-dispensing log will be kept current for each participant and will contain the identification of each participant and the date and quantity of drug dispensed. All remaining unused investigational product will be returned to the sponsor or sponsor's representative after study termination, or destroyed with the permission of the sponsor in accordance with applicable law and study site procedures. If investigational product is to be destroyed locally, the investigator will provide documentation in accordance with sponsor's specifications.

All records regarding disposition of the investigational product will be available for inspection by the clinical trial monitor.

5.6 ASSESSMENT OF COMPLIANCE WITH STUDY MEDICATION

Pill counts will be used to assess participant compliance with daily doses of the study medication.

6. STUDY PROCEDURES

6.1 INTENSIVE DIABETES MANAGEMENT

During the study, all participants will receive “intensive” management of their diabetes, and HbA_{1C} will be assessed every 3 months to evaluate metabolic control. The goal of treatment will be to maintain the HbA_{1C} level as close to normal as possible, without frequent occurrence of hypoglycemia. All individuals should strive for targets in accordance with current ADA recommendations, with HbA_{1C} levels of less than 7% in adults and less than 7.5% in adolescents (age 12–17 years), and with preprandial glucose levels of 90–130 mg/dL (plasma), postprandial levels of less than 180 mg/dL, and bedtime levels of 110–150 mg/dL.¹⁷⁸ All participants will be expected to take a sufficient number of daily insulin injections to meet the glycemic targets. In general, the expectation is that all participants will receive at least three injections of insulin daily, including short- and long-acting insulin preparations, or will utilize continuous subcutaneous insulin infusion (CSII insulin pump). Glucose levels should be checked at least four times daily. After reviewing these records, the diabetes management team will contact the treating physician about possible adjustments in the insulin regimen, referral to a registered dietitian, or other approaches that the diabetes management team believes would improve the glucose control if necessary. Records of glucose measurements and communication with the participant will be kept as source documentation. Participants will be contacted by the diabetes educator every 2 weeks

between visits to assess their diabetes. In addition, insulin use and hypoglycemic events will be captured at each visit on the appropriate CRFs. Participants will be required to record the amount of insulin they have used during the 5-day period immediately preceding each study visit. Insulin use logs will be provided to participants at each study visit and collected at the next visit. These logs will serve as the source documents.

6.2 RANDOM ASSIGNMENT, BLINDING, AND UNBLINDING

6.2.1 Random Assignment

Participants who sign the informed consent and meet the eligibility criteria will be randomly assigned in a 2:1 ratio to either the experimental or control group. A central automated randomization system will be used for treatment assignment and to create a unique identifier for each new study participant. Random assignment will be stratified according to site.

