9.1 PRIMARY OUTCOME AND ANALYSES

The primary outcome of each participant is the area under the stimulated C-peptide curve (AUC) over the first 2 hours of a 4-hour mixed meal glucose tolerance test conducted at the one-year visit. The AUC is computed using the trapezoidal rule that is a weighted sum of the C-peptide values over the 120 minutes. By the mean value theorem of integral calculus, the weighted mean C-peptide in pmol/mL is simply AUC/120.

The primary statistical hypothesis to be assessed in the study is whether:

- The mean C-peptide value for study subjects receiving imatinib is significantly higher than the mean value for placebo subjects.

The primary analysis will employ the weighted mean derived from the 2 hour AUC for each participant transformed as $\log(\text{mean C-peptide}+1)$. The comparison between the two treatment arms will be based on a t-test of treatment effect in an ANCOVA model adjusting for gender, baseline age and baseline $\log(\text{C-peptide}+1)$ ¹⁹⁰.

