9.2 SECONDARY OUTCOMES AND ANALYSES

Additional analyses of the primary outcome will include:

- A log rank test of the difference in the hazard function between groups in the incidence of the loss of the 2 hour peak C-peptide < 0.2 pmol/ml on a semi-annual MMTT ¹⁹¹, and
- Longitudinal analyses using mixed effects models with a random intercept and slope of the C-peptide values over the post-treatment period, adjusted for the baseline level of C-peptide. The average intercept and slope will be compared between groups adjusting for age, gender and the baseline $\log(C\text{-peptide}+1)$.

Additional secondary objectives are to examine how imatinib affects the following:

- Mean area under the stimulated C-peptide curve (AUC) curve at 12 months
- Mean area under the stimulated C-peptide curve (AUC) over 4 hours at 24 months
- HbA1c levels over time
- Insulin dose (units/kg) over time
- Number of severe hypoglycemic events
- Number and severity of adverse events

The mean levels of quantitative variables (e.g. HbA1c and insulin dose) over all follow-up values will be compared between groups using a normal errors longitudinal analysis.

The prevalence of a binary characteristic (e.g. yes/no or positive/negative) at a single visit (e.g. a history of hypoglycemia during follow-up) will be assessed using a logistic regression model. The prevalence of a binary characteristic over time will be assessed using generalized estimating equations.

The rates of severe hypoglycemic events and severe adverse events will be computed (total number of events divided by total patient years of follow-up) and the rates compared using a Poisson regression model, allowing for over-dispersion using a quasi-likelihood model as appropriate. Tests of significance will employ a robust estimate of the variance.

The above analyses will also be conducted to adjust for age, gender, baseline $\log(C\text{-peptide}+1)$ and baseline HbA1c; and by race/ethnicity, as appropriate. Analyses will also be conducted to examine the effect of HLA or other genotype.

Analyses will also be conducted to assess heterogeneity of the effect of treatment group (the group difference) as a function of age, gender, baseline $\log(C\text{-peptide}+1)$ and baseline HbA1c; and by race/ethnicity and HLA or other genotype. Heterogeneity will

be assessed using a test of treatment group by covariate interaction in an appropriate regression model.

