9.4 SAMPLE SIZE AND POWER CALCULATIONS

The primary analysis will compare the difference between the treated group versus the placebo group in the levels of the 2 hour AUC-mean using the $\log(\text{mean C-peptide}+1)$ in an ANCOVA model adjusting for gender, baseline age, and baseline $\log(\text{C-peptide}+1)$. Estimates of $\log(\text{mean C-peptide}+1)$ and root mean square error (RMSE) in the placebo group were obtained from prior studies. Among subjects with baseline C-peptide > 0.2 pmol/ml and age ≤ 21 years, the mean $\log(\text{C-peptide} + 1)$ values is 0.306 with RMSE = 0.185.

The planning parameters for the protocol were based upon the inclusion of adults and children. Unfortunately, the FDA has declined the request to lower the age and, therefore, the study will only enroll adults at this time.

Hence, it is appropriate to revisit the design of the study in light of restricting the eligible population to be age 18 and over. In previous studies, it has shown the older a participant is, the lower the rate of C-peptide loss. This means that the current design of detecting a one-year C-peptide projected level 45% greater than expected on the control arm corresponds to an increase in C-peptide over the baseline value at enrollment, which is not practical. However, analyses completed after this study was initially designed indicate that the appropriate variance estimate to use for the sample size calculation should be smaller than what was used in the current design. This has the net effect of increasing the sensitivity of the trial to detecting an effect size smaller than the advertised value in the current design.

Using standard equations for the comparison of two means, a sample size of 40 Imatinib treated and 20 placebo treated subjects with complete data needed for the primary analysis, would provide power of 85% to detect a 0.35 increase in the mean $\log(\text{C-peptide} + 1)$ (0.306 vs. 0.445, which corresponds to 75% of the RMSE) in the experimental treatment group using a two-sample T- test at the 0.05 level (one-sided).

Assuming that 10% of the subjects will have missing data (one-year MMTT was not done or subject withdrew prior to the one-year assessment), the sample size goal for

this study is 66 subjects (46 + 22). Should the number with missing data exceed 10%, the study will enroll additional replacement subjects as needed.

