9.5 INTERIM MONITORING PLAN

For purposes of the 6-month analysis, a trend for benefit would be an outcome that does not exclude a significant result being achieved at the end of Phase 2 with a twelve month outcome as specified by the protocol. Changes from baseline in stimulated C-peptide mean AUC in T1D patients on placebo have been reported as approximately 30% at 6 months ([Orban et al 2011](#)³⁹, [Raz et al 2007](#)¹⁹⁴). Sample size calculations were thus based on the assumption of a ~30% treatment effect at around 6 months of treatment and a standard deviation for baseline- and placebo-adjusted stimulated C-peptide mean AUC of 0.39 nmol/liter/2h (Greenbaum et al 2012). In this case, an interim analysis will calculate the conditional power after 21 participants have been evaluated. Based upon the table that follows, should the calculated interim Z value be greater than or equal to 0.8, the conditional power would be estimated to be at least .26 and .74 if the true effect is as assumed under the alternative hypothesis at study conclusion. Therefore, a threshold will be set on the conditional power as the level-of-proof that the difference in stimulated C-peptide mean AUC between gleevec and placebo is of presumed benefit to allow the study to move forward to phase two.

Table of Conditional Power Assuming an Alternate Effect Size (defined as $(\mu_1 - \mu_0)/2(sd) = 0.37$, an interim analysis at 21 patients and a final analysis at 66 patients. Two-tailed alpha = 0.05

Interim Z Value	Conditional Power	Conditional Power
	Under Observed Trend	Under Protocol Assumed Effect
0.0	<.01	.54
0.4	.06	.65
0.8	.26	.74
1.2	.58	.82
1.6	.86	.89

Additional interim analyses will be conducted when 50% of the targeted number of study subjects have reached the planned end point (i.e., one year of follow up) and will be reviewed by the Data and Safety Monitoring Board (DSMB) for assessment of effectiveness and safety. If a group sequential stopping boundary is crossed, the DSMB may recommend termination of the trial early. The Lan-DeMets¹⁹⁵ spending function with an O'Brien-Fleming boundary will be used to protect the type I error probability for the primary outcome analyses, and to assess the significance of the interim results

periodically during the trial. The spending function that approximates the O'Brien-Fleming boundaries is:

$$\alpha_1(t^*) = 2 - 2\Phi\left[\frac{Z_{\alpha/2}}{\sqrt{t^*}}\right]$$

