- Long-acting basal (such as glargine) insulin or continuous subcutaneous insulin infusion may be administered before, during and after the test as usual. Participants on glargine may take their usual injection at the appropriate time, and those on

continuous subcutaneous insulin infusion may continue with their usual basal settings.

Target Glucose Level at the Start of Test

The target glucose level at the start of the test is between 70 and 200 mg/dL. Regular insulin or short acting insulin analogues may be used up to 6 and 2 hours before the test, respectively, to achieve the desired glucose level. The investigator and the study participant should discuss the individual situation for insulin administration to attain the goal of meter capillary glucose values within the range of 70–200 mg/dL at the start of the test. For example, as a practical matter, participants may be instructed to check their blood glucose by meter at home 2 hours before the start of the test so that marked hyperglycemia can be treated with a short-acting insulin analogue. Alternatively, participants who arrive at the research unit with elevated blood glucose can receive additional short-acting insulin analogues at the time of their arrival, if the test itself does not start until at least 2 hours after insulin administration and occurs before 10 a.m.

IV Placement During the Test

- The IV should be in place for the duration of the test and must be flushed after each draw with saline solution or heparin flush.
- The participant should remain sitting or resting in bed quietly throughout the test and until the test is completed. However, he or she may engage in quiet, non-strenuous activities, such as reading, playing cards, or watching TV. The participant may walk to the bathroom between blood draws if necessary.

Testing Instructions

Time Point –10 minutes

- The first sample should be taken at least 10 minutes after establishing the line(s) and when the participant is calm and relaxed (if possible, depending on age) - this is the “–10 minute” sample.

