- Spin the collection tubes. Then transfer the plasma into individual vials. Please make sure that each vial is properly identified with a label that indicates the time point.
- Freeze the samples for glucose, C-peptide levels, and glucagon/proinsulin.
- Ship the glucose and C-peptide specimens to the laboratory where the assays will be performed.
- Ship the glucagon/proinsulin specimens to the laboratory where the samples will be stored until testing is initiated at the end of the study.

A clogged line, missed sample, or other deviation from the protocol must be noted on the Comments section of the MMTT specimen transmittal form.

Time (minutes)	Glucose Sample Taken	C-peptide / Sample Taken
-10	X	X
0	X	X
Participant drinks Boost [®]		
15	X	X
30	X	X
60	X	X
90	X	X
120	X	X
150	X	X
180	X	X
210	X	X
240	X	X

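### Randomisation is stratified by site but the primary and adjusted secondary models omit site: a minor efficiency loss if allocation is balanced within site and sites differ

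*Combined protocol and SAP*

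**What the plan says.** Section 6.2.1 describes central automated 2:1 allocation and then states: "Random assignment will be stratified according to site". No other factor is named, and neither a block scheme nor any other within-site balancing method is described.

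The primary comparison in 9.1 is a t-test of the treatment effect in an "ANCOVA model adjusting for gender, baseline age and baseline" log(C-peptide+1). Section 9.4 repeats the model for the sample size: "ANCOVA model adjusting for gender, baseline age, and baseline" log(C-peptide+1). Site appears in neither.

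In 9.2 the longitudinal C-peptide model adjusts for age, gender and baseline log(C-peptide+1). A further set of adjusted analyses is announced ("The above analyses will also be conducted to adjust for age, gender, baseline" log(C-peptide+1), then baseline HbA1c, with race/ethnicity where appropriate). Site is absent from these models and from the list of treatment-by-covariate interaction tests.

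Section 9.5 carries the primary test into the interim plan: "Additional interim analyses will be conducted when 50% of the targeted number of study subjects have reached the planned end point". Both the efficacy boundary and the futility rule at that look rest on it.

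**The concern.** A design that balances treatment within site removes site differences from the treatment contrast. If the model has no site term, those differences stay in the residual. The standard error then describes a less efficient design than the one that was run, and the test rejects less often than its nominal level.

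Two conditions must both hold: allocation is balanced within site, and sites still differ after adjustment for gender, age and baseline C-peptide. If either fails, there is no conservatism. At stake are a point or so of power in a trial of about 60 evaluable participants, and a model choice that is better settled before unblinding than after.

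**Working it through.** **1. The plan's own power figure.** Inputs from 9.4: means 0.306 and 0.445 (difference 0.139), RMSE 0.185, 40 + 20 evaluable, one-sided 0.05.

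- SE = 0.185 × √(1/20 + 1/40) = 0.0507, and 0.139/0.0507 = 2.744.
- Normal approximation: Φ(2.744 − 1.645) = 86.4%. Noncentral t with 58 df: 85.7%.

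The stated 85% reproduces, without any site term.

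**2. Large-sample effect of omitting site, with perfect within-site balance.** Let ρ be the site share of residual variance (assumed) and k = √(1 − ρ).

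- True level without site: 1 − Φ(1.645/k).
- Power without site: Φ(2.744/k − 1.645/k).
- Power with site: Φ(2.744/k − 1.645).

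| ρ | Level without site | Power without site | Power with site |
|---|---|---|---|
| 0 | 5.0% | 86.4% | 86.4% |
| 0.05 | 4.6% | 87.0% | 87.9% |
| 0.10 | 4.2% | 87.7% | 89.4% |
| 0.20 | 3.3% | 89.0% | 92.3% |

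This is an upper bound on the effect. It ignores incomplete blocks, missing data and the degrees of freedom spent on site.

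**3. Simulation of the final analysis.** From 9.4: 66 randomised 2:1, about 10% missing (60 completers), effect 0.75 RMSE, one-sided 0.05. Assumed: missing at random; three noise covariates; total residual variance fixed at 1; blocks of 3 or 6 within site, or none; and four site layouts (6 sites of 11; 11 sites of 6; uneven layouts of 10 and of 15 sites). Sites with fewer than 6 randomised are pooled. There were 100,000 trials per cell, so the simulation SE is at most 0.07 points for level and 0.12 for power.

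| ρ | Level without site, blocked | Power change from adding pooled site, blocked |
|---|---|---|
| 0 | – | −0.7 to −1.1 points |
| 0.05 | 4.6–4.8% | −0.2 to +0.2 |
| 0.10 | 4.3–4.6% | +0.5 to +1.2 |
| 0.20 | 3.6–4.1% | +1.8 to +3.3 |

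With blocking, power without site is 83.5–86.4%. Unpooled site effects at ρ = 0 cost 0.7 to 6.1 points, which is why pooling matters.

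With no within-site blocking, the level without site is 4.9–5.1%, so there is no conservatism. Adding pooled site then changes power by −2.5 to −7.2 points at ρ = 0, −0.1 to −3.7 at 0.10 and −0.3 to +2.7 at 0.20.

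**4. The 50% look.** Assumed: 33 participants (half of 66), all evaluable, blocks of 3, 40,000 trials per cell. The spending function printed in 9.5 gives, at t* = 0.5, 2 − 2Φ(1.960/0.707) = 0.0056 for α = 0.05 and 2 − 2Φ(1.645/0.707) = 0.020 for α = 0.10. Both were used as the one-sided level. Power without site is 22.3–23.7% and 41.5–43.2% respectively. Change from adding site, over both levels:

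| ρ | Pooling rule re-applied at the look | Final strata reused |
|---|---|---|
| 0 | 0.0 to −1.0 points | −1.8 to −6.7 |
| 0.10 | 0.0 to +1.3 | −2.9 to +1.5 |
| 0.20 | +0.1 to +3.9 | +1.4 to +5.6 |

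The futility rule and the secondary models were not simulated.

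**The case against.** The strongest reply is that a prespecified ANCOVA on three covariates is valid without site, and that every quantity driving the gain is assumed. Much in the documents points to a low site share. Glycaemic targets are common ("All individuals should strive for targets in accordance with current ADA recommendations"). Appendix 2 fixes the drink, the fasting limits, the sampling times and the handling; it sets a starting range ("The target glucose level at the start of the test is between 70 and 200 mg/dL") and sends samples away for assay ("Ship the glucose and C-peptide specimens to the laboratory where the assays will be performed"). Baseline C-peptide is already a covariate. At a share of 5% or less the site term gains about nothing or costs up to about a point, and without within-site balance it can cost several.

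Most of this stands, and it keeps the point minor. It does not remove it. Section 3.6 says C-peptide is affected by glycaemic control, and under 6.1 insulin adjustment goes through each participant's treating physician. That care follows randomisation, so a baseline covariate cannot fully absorb it. A non-zero site share is plausible, though not shown. Stratified allocation also ordinarily means balance within site, so the costly unblocked case is the less natural reading of 6.2.1.

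A second reply also stands: block sizes must not be printed in a protocol that sites read. With known blocks of 3 at 2:1, the third assignment is always determined by the first two, and the second is determined whenever the first is placebo (probability 1/3). So (1 + 1/3)/3 = 44% of assignments would be predictable to someone who knew the earlier ones.

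**Conclusion.** The omission of site from the primary and adjusted secondary models is plain in the text and unexplained. If allocation is balanced within site and sites differ after adjustment, the one-sided 0.05 test runs at about 4.3–4.6% for a 10% site share and 3.6–4.1% for 20%. Adding pooled site would gain about 1 point of power at a 10% share and 2–3 points at 20%. These figures rest on assumed site layouts, block sizes and site shares.

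A reader might infer that leaving out the stratification factor biases the estimate, inflates type I error or leaves the trial underpowered. The documents support none of these. The estimate is unbiased, any error in the level is towards caution, and with blocking the simulated power without site (83.5–86.4%) is close to the planned 85%. Nor do the documents show that the test is in fact conservative, because they establish neither within-site balance nor a site difference. This is a minor point of efficiency and consistency.

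**What to change.** 1. Confirm in 6.2.1 that allocation is balanced within site. Record block sizes only in a restricted randomisation document that sites cannot see.
2. If it is balanced, add site as a fixed factor to the primary ANCOVA in 9.1 and to the same model in 9.4. Pool small sites by a rule based on the number randomised, not on completers, and fixed before unblinding.
3. Use the same covariate set for the adjusted C-peptide models in 9.2 and for both the efficacy and the futility test at the 50% look. Re-apply the pooling rule to the participants counted at that look.
4. Keep the model without site as a sensitivity analysis.
5. If allocation is not balanced within site, keep the primary model as written and say why site is left out.

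Cost: one model term, one pooling rule applied at two time points, one sensitivity analysis and one entry in a restricted document. If sites do not differ, the final analysis loses about 1 point of power and the 50% look 0 to 1 point with re-pooling (1.8 to 6.7 if the final strata were reused). Item 5 matters because without within-site balance the site term could cost 2.5 to about 7 points when sites do not differ. The effect on the futility rule was not computed. That rule depends only on the sign of the test statistic, and near-balance within site leaves the treatment estimate almost unchanged, so a large effect is not expected.
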